6.1.2 Size of sample

We will aim to recruit 10-15 GPs, 10-15 clinical pharmacists and pharmacy technicians and 10-15 patients. As we are aiming to include one role/patient from each practice we will therefore aim to include 10-15 general practice sites in total. We will move away from conceptualisations of 'data saturation', which are contested within the qualitative literature, and instead of focussing on the number of interviews conducted, we will focus on the quality of the sample, the interview content, and data triangulation to enrich our findings.(25) This approach will focus on evaluations of sample size sufficiency and theme saturation in terms of data adequacy and 'information power' rather than the number of interviews conducted.(26, 27) Our approach using Grounded Theory methods will also allow us to triangulate and compare and contrast the interviews between different participant groups.

6.1.3 Inclusion criteria

For patients

- Over 18 years old
- At least one GP and pharmacist appointment in the past year
- Able to freely give informed consent

Clinical pharmacists and pharmacy technicians

• Experience of caring for patients with long-term conditions and/or multimorbidity, for example in a diabetes clinic

GPs

- Experience of appointments (face-to-face/online/telephone) within the past six months
- At least one year's experience of working in general practice

6.1.4 Exclusion criteria

Patients

• Identified by practice research contact as being unsuitable for interview because of communication difficulties, welfare issues, 'decline contact' noted on patient record, lacking capacity to consent (for the patient) or safety issues (for the researcher)

Clinical pharmacists and pharmacy technicians

• No experience of caring for patients with long-term conditions and/or multi-morbidity

GPs

• Less than one year's experience of working in general practice

6.1.5 Recruitment

The South West Research Delivery Network (RDN) will support the recruitment of GP practices sites with engaged clinical pharmacists to participate in the research. This will be achieved through ongoing regular meetings with the CRN and the adoption of the Pharm-Connect study to the NIHR portfolio. A Research Information Sheet for Practices (RISP) will be developed by the research team to support with the initial recruitment of practice sites.

After initial engagement via the RDN, the RDN will e-introduce a named contact within the practice to the research team. The researcher will contact the practice to further explain the study aims and what is required from the practice, including:

- Identification of GPs and pharmacy staff for interviews
- Identification of patients for interviews

Patient participants

The practice study contact will coordinate a search of the practice computer system by practice staff to identify patients according to inclusion criteria.

The participating general practice (study contact or GP) will screen the list of potential participants to exclude anyone deemed unsuitable for interview on the following bases: communication difficulties, welfare issues, 'decline contact' noted on patient record, lacking capacity to consent (for the patient) or safety issues (for the researcher). Study packs containing an invitation letter, study information sheet and consent form will be posted from participating general practices until a required number of patients is reached.

Patients will be invited to contact the study researcher by email to discuss taking part in the study. The researcher will then contact the patient by phone to answer any questions and confirm that they would like to take part in the research. The researcher will take verbal consent from the potential participant and the participant will be sent a link to complete the consent form digitally using MS forms.

The researcher will arrange an interview appointment with participants, and the mode of interview (face-to-face/online/telephone) and location, if applicable, will be chosen by the participant.

Two weeks after the study packs have been posted from the practice, the research team will send (via secure transfer) the practice study contact a list of those patients who have consented to take part in the study so that s/he knows who to remind about the study.

The practice study contact will telephone potential participants who have not made contact with the research team within 2 to 3 weeks of the mailout from the practice. This contact is to remind potential participants about the study and provide them with an opportunity to take part in the research. If the practice study contact is not able to speak with the potential participant at the first attempt, s/he will make two further attempts to do so. To preserve confidentiality, no voicemail messages will be left.

GP and clinical pharmacist participants

The practice study contact will identify potential GP and clinical pharmacist participants who will be sent an invitation email, with study information sheet and consent form as attachments.

GPs and clinical pharmacists will be invited to telephone or email the study researcher to discuss taking part in the study. The researcher will take verbal consent from the potential participant and the participant will be sent a link to complete the consent form digitally using MS forms. The mode of interview (face-to face/online/telephone) and location, if applicable, will be chosen by the participant.

Two weeks after the invitation emails have been sent, the research team will send (via secure transfer) the practice study contact a list of those GPs/clinical pharmacists who have consented to take part in the study so that s/he knows who to remind about the study.

The practice study contact will telephone or email potential GP/clinical pharmacist participants who have not made contact with the research team within 2 to 3 weeks of receiving the original email about the study. This contact is to remind potential participants about the study and provide them with an opportunity to take part in the research. If the practice study contact is not able to speak with the potential participant at the first attempt, s/he will make two further attempts to do so. To preserve confidentiality, no voicemail messages will be left.

6.2 Workstream 2

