4.1.1 Sample and recruitment

We will sample GPs, clinical pharmacists, pharmacy technicians and patients from practices in the South West of England which promote a continuity of care approach through the Research Delivery Network.

We will target general practices from catchment areas with higher densities of patient deprivation, or those practices identifying as part of 'Deep End' networks for recruitment to the professional and patient interviews. Mortality, hospital admissions and multimorbidity rates are higher in deprived areas, while patient satisfaction with general practice is lower in these areas, and we want to ensure we capture the experiences of those working and receiving care in this context.(22-24)

We will aim to recruit 10-15 GPs, 10-15 clinical pharmacists and pharmacy technicians and 10-15 patients. We will move away from conceptualisations of 'data saturation', which are contested within the qualitative literature, and instead of focussing on the number of interviews conducted, we will focus on the quality of the sample, the interview content, and data triangulation to enrich our findings.(25) This approach will focus on evaluations of sample size sufficiency and theme saturation in terms of data adequacy and 'information power' rather than the number of interviews conducted.(26, 27)

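### Section 6.1.5 gives patients no stated offline way to reply or to complete consent, and the list sent to the practice cannot support its own reminder rule

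*Protocol*

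**What the plan says.** The patient route is in Protocol section 6.1.5 (Workstream 1), under patient participants. The invitation is on paper: "Study packs containing an invitation letter, study information sheet and consent form will be posted from participating general practices". The reply is electronic: "Patients will be invited to contact the study researcher by email to discuss taking part in the study". A telephone step follows that email: "The researcher will then contact the patient by phone to answer any questions". The researcher takes verbal consent, and then "the participant will be sent a link to complete the consent form digitally using MS forms". The patient chooses the interview mode, which may be face-to-face, online or by telephone.

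For professionals the same section is wider: "GPs and clinical pharmacists will be invited to telephone or email the study researcher to discuss taking part in the study".

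Two weeks after posting, the research team sends the practice contact "a list of those patients who have consented to take part in the study so that s/he knows who to remind". The practice contact then telephones patients who have not been in touch with the research team, with two further attempts if the first does not reach them.

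Section 4.1.1 explains the targeting of practices in more deprived catchments: "we want to ensure we capture the experiences of those working and receiving care in this context". Sections 6.1.1 and 6.1.2 plan one patient per practice and 10-15 patients in total.

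**The concern.** A patient can be invited by post and interviewed at home or by telephone, yet both steps in between, replying and completing consent, are described only in digital form. The narrower reply route falls on patients, and no reason is given. Lack of email or internet access is not among the exclusion criteria in section 6.1.4, so any filter is unintended and would not be visible in the reported eligibility criteria.

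What is at stake is objective 2, patient perceptions of continuity. Sections 4.1.1 and 6.1.2 rest the adequacy of the sample on its quality rather than on the number of interviews, so the route by which patients enter bears on the study's own standard. If some patients are missed at recruitment, the analysis cannot restore them.

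The reminder step has a separate problem. The information given to the practice does not match the rule that the practice has to apply.

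**Working it through.** The study has no power calculation or numerical claim on this point, so the check sets the provisions side by side.

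**Patient pathway, step by step (section 6.1.5)**

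| Step | Route stated for patients | Possible without internet access as written? |
|---|---|---|
| Invitation | Posted pack, including a consent form | Yes |
| Reply to researcher | Email | No |
| Discussion and verbal consent | Telephone call, after the email | Yes, but only once the email has been sent |
| Completing the consent form | MS Forms link | No; no use or return route is stated for the posted form |
| Reminder | Telephone call from the practice | Yes, but the hand-over to the researcher is not described |
| Interview | Face-to-face, online or telephone | Yes |

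The reply and the completion of consent are the two steps with no stated offline form. The reminder call bypasses the first only if someone passes the patient's agreement to the researcher, and it does not bypass the second.

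**Comparison with professionals.** They may telephone or email ("GPs and clinical pharmacists will be invited to telephone or email the study researcher"). Their consent form is also completed through MS Forms, but their invitation itself arrives by email, so the link needs no access that the invitation did not already need. The patient invitation is on paper, so for patients the link does add a requirement.

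**Sample.** With one patient per practice and 10-15 patients, each patient supplies between 1/15 = 6.7% and 1/10 = 10% of the patient interviews, and all of the patient interviews for that practice. Section 6.1.1 lists characteristics to vary among GPs and pharmacy staff (experience, ethnicity and, for pharmacy roles, qualifications). It lists none for patients, so no stated sampling criterion would offset an imbalance in who replies.

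**Size.** The Protocol gives no figure for patients without email or internet access, overall or in deprived catchments. The extent of under-representation therefore cannot be calculated.

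**Reminder rule.** Two weeks after posting, invited patients fall into four groups:

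1. replied and consented;
2. replied and declined;
3. replied and still undecided;
4. not replied.

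The rule calls for telephoning group 4 only. The list identifies group 1 only. Removing group 1 from the mailing list leaves groups 2, 3 and 4 mixed together, and the practice has nothing with which to separate them. The professional reminder in the same section has the same mismatch.

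**The case against.** The strongest answer is that the practice telephones patients who have not been in touch, to offer them the chance to take part. That call needs no internet access and goes to the patients who might otherwise be missed. Verbal consent is taken, a paper form is in the pack, and nothing says that paper will be refused. The invitation letter, which would carry the actual contact instructions, is not in view. This stands as far as it goes: the offline patient has a partial route. It does not close the gap, because the hand-over after the call is not described and the link is the only stated way to complete consent.

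Several stronger readings are tempting but not supported:

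- A reader might infer that offline patients are screened out. The reminder call and the absence of a digital-access exclusion mean that only a risk of under-representation can be claimed.
- A reader might infer that the first patient to email in each practice is the one interviewed. The text says when posting of packs stops; it states no first-come selection rule.
- A reader might infer that patients who decline will be called three times. The rule as worded excludes anyone who has replied, and further attempts follow only when the first did not reach the patient. The defect is that the practice cannot tell who has replied.
- A reader might assume that patients are the group least likely to be online, or put a percentage on those offline. The Protocol supports neither.
- A reader might take the study to be confined to deprived practices. Section 6.1.1 also includes the least deprived locations.

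**Conclusion.** The point holds as a gap in the stated recruitment route. Section 6.1.5 describes no offline means for patients to reply to the researcher or to complete consent, and the reminder call offsets this only in part. Followed as written, it risks under-representing patients without digital access in a sample of 10-15, which sits badly with the reason that section 4.1.1 gives for targeting deprived catchments. This rests on the assumptions that some eligible patients lack such access and that the study materials add no other route. The size is unknown and cannot be estimated from the document.

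The reminder mismatch is a separate, definite inconsistency: a list of consenters does not let the practice identify those who have not replied, so a patient who has declined or is undecided may be telephoned.

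Both are worth correcting before packs are posted.

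**What to change.** In section 6.1.5 (Workstream 1), and in the invitation letter to match:

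- Let patients reply by telephone or prepaid slip as well as by email.
- Accept the posted paper consent form, returned by post or signed at the interview, or recorded verbal consent, as equivalent to MS Forms, subject to REC approval.
- State how a patient's yes on the reminder call reaches the researcher, for example by the practice contact passing on a telephone number with the patient's permission.
- Replace the list of consenters with a do-not-remind list of everyone who has replied, without showing the decision. Do the same for professionals.

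The cost is a study telephone number, a small amount of postage, and secure storage for some paper forms. If approval is already in place, the change also needs an amendment through the sponsor, HRA and REC under section 7.2.

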6.2.1 Sampling

Nominal group technique approaches typically require a sample of people who have experience, expertise and insight into the problem being explored. For this project, participants will include:

- GPs
- Pharmacists and pharmacy technicians working in General Practice
- Pharmacy medicine optimisation leads, workforce leads, or primary care leads

- Researchers/academics and data scientists using big data and looking at continuity of care for research purposes
- Other participants, including other ARRS role team members, as identified during the project development phase and from PPI input

We will also invite feedback on the NGT results from our PPI group, however, they will not attend the group as professional participants.

6.1.2 Size of sample

We will aim to include 8-12 professional members to the NGT meetings. The sample needs to include a range of expertise, but also a number of participants that will allow useful discussion within the constraints of a meeting.

6.1.3 Inclusion criteria

The inclusion criteria will be kept broad to allow us to include participants across general practice, pharmacy roles, primary care research and other members of the general practice multi-disciplinary team.

6.1.4 Exclusion criteria

We will exclude participants who are unable to provide informed consent to participate in the meeting.

6.1.5 Recruitment

We will use our professional networks to recruit participants to the NGT meeting. The project team is comprised of academic GPs, pharmacists and primary care researchers, and we will target specific participants working in these areas and in continuity of care measurement research and known to the research team to target for their expert advice in the NGT meetings.

The research fellow will email the known contacts with an initial invitation to participate in the NGT meeting. The researcher will take consent from the potential participant (using the consent form) and will arrange a meeting date and time suitable for participants. We are aware that it may be difficult to arrange a time suitable for all 8-12 participants and will consider whether we need to hold two different meetings to allow each participant to attend. We will agree the mode of the NGT meeting (face-to face or online using Microsoft Teams) and location with all participants. Where some participants prefer a face-to-face meeting and others prefer an online meeting, we will arrange a 'hybrid' NGT meeting allowing for some participants to join remotely.

7. ETHICAL AND REGULATORY CONSIDERATIONS

Over the course of the study, we will work to align methodologies and conduct to the UK Policy for health and social care research, in order to protect members of the public and professionals involved in the research. A number of potential risks have been identified, which will require appropriate management and mitigation: • Data Management

A secure chain of data handling from the point of collection at research sites to being received, processed and stored by the research team at the University of Exeter will be in place to ensure that interview recordings are handled and stored in an appropriate manner. Field recordings will be taken using an encrypted audio recorder or through a secure University of Exeter Teams account (for remote interviews. The data extracted from patient, pharmacy role and GP profiles and anonymised audio recordings from Workstream 1 will be stored on a dedicated, secure, restricted access University of Exeter SharePoint site for the duration of the study, which only the research team and data custodian will have access to. Workstream 1 interview recordings will only be stored for up to 90 days after recording to allow anonymised transcriptions to be made using Microsoft Word or Microsoft Teams auto-transcibe. After this period, the recorded interview files will be deleted.

• Participant disclosures

The research topic is unlikely to provoke recall of traumatic events or upsetting memories during qualitative interviews however, due to the unpredictable nature of responses from participants, this is not a risk that can be eliminated entirely. The interviews will be conducted by an experienced post-doctoral researcher who has experience of conducting qualitative interviews and is familiar with signs and nonverbal cues that may indicate participants are in distress or significantly upset. The interviewer will proactively work to avoid and minimise any upsetting topics of discussion however, if a participant does become distressed, they will be offered the opportunity to terminate the interview at any point.

• Time incumbency

Given the current pressures and demands on the health system in the UK, we acknowledge that an hour-long interview is not an insignificant time commitment for GPs and practice-based pharmacy staff. The research team will make every effort to ensure that interviews take place at a time that is convenient to participants and do not impinge on daily clinical practice. The £75 incentive for professional participants recognises the time commitment made by participants to contribute to this research study. We have also costed in time for patient participation in interviews at £50 per interview (based on NIHR Involve payment guidelines for patient and public involvement).

7.2 Research Ethics Committee (REC) and other Regulatory review & reports

Health Research Authority (HRA) approval will be sought before the commencement of any research activity detailed in this protocol. As part of this approval process, a favourable NHS Research Ethics Committee (REC) decision will need to be in place. The participant information sheets, consent forms, topic guides and other relevant documents will be submitted for review as part of this process. All correspondence with the REC will be retained for information. The REC will be informed when the study ends.

Regulatory Review & Compliance

The Chief Investigator (CI) will ensure that appropriate approvals and confirmations are in place with the participating primary care organisations before sites commence enrolment of patients, GPs and pharmacy staff into the proposed research. Specific arrangements on how to gain approval from participating organisations will be in place and comply with the relevant guidance for NHS sites. For any amendment to the study, the CI, in agreement with the sponsor, will submit information to the appropriate body in order for them to issue approval for the amendment. The CI or research post-doctoral fellow will work with sites (both the NHS sites and the research team based at the University of Exeter) to put the necessary arrangements in place to implement the amendment to confirm their support for the study as amended.

Amendments

Any proposed substantial or non-substantial amendments to the study will be shared with the HRA and REC for consideration after discussion with the supervisory team and the sponsor. The sponsor will decide whether an amendment is substantial or non-substantial for the purpose of submission to the REC. Once approved, any participating sites, the research team and the supervisory group will be notified of any amendment details. The amendment history will be documented through retention of all documents pertaining to application for amendment and correspondence with the relevant stakeholders (i.e. the sponsor, REC, research sites) over the course of application and implementation of any amendments.

7.3 Peer review

The research programme underwent extensive peer review as part of the grant application process.

7.4 Patient & Public Involvement

Patient and public involvement (PPI) with the proposed research will be critical to ensure that the planned research is meaningful to patients and adequately informed by representatives of patients who receive general practice-based care. We will use the Public

Involvement in Research Impact Toolkit (PIRIT) which is a set of tools, including a planning tool, to help plan and incorporate public involvement in the research, and track the contributions made in each interaction and meeting.(35) The PIRIT tracking tool also provides a log to allow us to record the impact of public involvement in this project against the UK Standards for Public Involvement.

We have established a PPI group across three different projects related to continuity of care being conducted in Exeter. Working with the same group of people will allow us to build longitudinal relationships and capacity within the PPI team, and better understand through different projects the patient's perspective on what is important for them in experiencing continuity. This PPI group will advise and work with us throughout the course of this project. Specifically, the PPI group involving patients will be involved in the interview development and analysis. We will conduct 'mock interviews' with members of our PPI group to inform our patient interview guides. We will ask members of our PPI group if they would like to be involved with transcript coding, and what training if any they need to be able to do this. We will invite interested PPI members to code selected transcripts and join the team during analysis meetings to help develop the themes, theories and approach to disseminating the results. We will also discuss the interview guides with our pharmacy lead collaborators for comment.

The PPI group will meet routinely, likely 3-4 time over the course of the study and based around the preferences of the group. We will work with our PPI group to inform our dissemination strategies across each of our continuity of care projects.

